For the first question, predefined parameters such as sample size, capacity building, acceptance by community-dwelling older people (participants) and care providers were examined.

3. Research methods

Prospective randomized controlled study. A total of 2000 community-dwelling older persons aged 60 and above at-risk of functional loss in Chaoyang District of Beijing are recruited and randomly assigned to the intervention group (n=500) and control group (n=1500).

3.1. Primary Outcome Measure:

Feasibility of implementing the ICOPE program in China:

- 1) Sample size (to successfully recruit over 2,000 participants, 500 of whom were to be categorized in the intervention group)
- 2) Capacity building (at least 200 primary care providers to be fully trained and deployed in the pilot program)
- 3) Acceptance (reach more than 90% satisfaction with the pilot by both participants and providers).

3.2. Secondary Outcome Measures:

Independence - measured by the activities of daily living (ADL) 14-questionnaire scale, to assess the participant's physical function.

Cognition - measured by mini-mental status examination (MMSE) to assess the cognitive health of the participants.

Vitality - nutrition measured by mini-nutritional assessment- short form (MNA-SF) to assess the risk of malnutrition.

Mobility - measured by short physical performance battery (SPPB) to assess the risk of declining mobility.

Psychological health - measured by geriatric depression scale-five items (GDS-5) using a short set of questions to assess possible depressive symptoms.

4. Statistical methods and sample size

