4.1. Sample size calculation

At present, there is no specific local data to support the calculation of sample size.

Using all-cause death and falls as the endpoint events, based on previous literature and pre-experimental data, the percentage of decline in intrinsic ability in the community elderly population as the dependent variable ranged from 43.0% to 77.4%, and the incidence of all-cause death, falls and functional decline in the group with decline in intrinsic ability at 3-year follow-up was 16.4%, 55.3% and 64.8%, respectively, using PASS software, setting a two-sided $\alpha=0.05$ with 90% certainty, based on the above data, it was calculated that at least 58 people with all-cause death as the endpoint event of decline in intrinsic ability, 72 people with falls as the endpoint event, and 126 people with decline in function as the endpoint event were required, considering that the population included in this study was elderly, and based on previous studies, the proportion of decline in intrinsic ability was estimated to be 70%, and considering a 5% loss of follow-up rate, at least 190 elderly people. Therefore, a total of 380 individuals were included in the intervention and control groups (intervention community and control community).

This project plans to investigate and follow up with at least 2000 older people and intervene in more than 500 cases. Combined with the sample size calculation above, this project should meet the needs of sample size.

4.2. Statistical methods:

STATA will be used to establish the database and conduct statistical analysis.

The baseline data were collected, and the corresponding statistical methods were selected according to the data type to compare the basic clinical information of patients: if the data conformed to the normal distribution, it was expressed as the mean \pm standard deviation ($\pm s$),

and the independent sample t test was used for the comparison between the two groups; If the data does not conform to the normal distribution, it is expressed as the median (25th percentile, 75th percentile), and the Mann Whitney U test is used for the comparison between the two groups.

The intervention group and the control group were propensity matched, and the incidence of adverse health outcomes (all-cause death, falls, functional decline) and changes in quality of life (self-control, comparison between the two groups) were compared between the two groups.

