5.2 Randomization

A random number table (1-2000 random order) was established and managed by a dedicated person (who was only responsible for informing the number). The older person who met the enrollment conditions received random numbers according to the order of the random number table. The random number divided by 3 is an integer, and the remaining 1 is the control group, and the remaining 2 is the intervention group.

6. Research process

6.1 Data acquisition and observation indicators:

- (1) The elderly who met the inclusion criteria were included, and their demographic characteristics (gender, age, education, height, weight, BMI, smoking and drinking history) were recorded
- (2) Assessment of intrinsic ability: according to the screening tool for integrated care for older people (ICOPE) and the people-centered assessment guide issued by WHO, there are five dimensions in total, with 1 point for each dimension. Impairment in any dimension is defined as a decline in intrinsic ability. See Case Report Form (CRF) for the rating scale of each dimension.

Cognitive dimension: Mini Mental State Examination (MMSE), with a total score of 30 points. According to the education level of the research object, whether there is cognitive dysfunction is defined. Illiteracy ≤ 17 points, primary school level ≤ 20 points, secondary school level (including technical secondary school) ≤ 22 points, university level (including junior college) ≤ 23 points. Vitality: the mini nutritional assessment short form (MNA-SF) has

a total score of 14 points. A score of 12-14 defines normal nutritional status, 8-11 indicates malnutrition risk, and 0-7 indicates malnutrition.

Psychology: the total score of the geriatric depression scale 15 item (GDS-15) is 15 points, and a score of ≥ 5 points is defined as depression (Appendix 3). Or the Zung Depression Scale (SDS) was used for evaluation. Standard score = total score \times 1.25, take an integer, and a standard score > 50 points is considered as depression.

Exercise: the short physical performance battery test (SPPB), including the evaluation of sitting up test, gait speed test and balance test, has a full score of 4 points for each part, a total score of 12 points, and a score of ≤ 9 points is considered as physical function decline.

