6.3 Follow-up

Follow-up time: 3 Months, 6 Months from baseline

Follow up will be carried out through telephone, family doctor visit, medical record system review, and the ADL score, frailty scale score, and adverse health outcomes (falls, recurrent falls, severe falls, all-cause death) were recorded.

Record the time of the first fall, which can be specific to month, such as December 2020. If the person or family member can't remember clearly, they can provide the time range, such as January to June 2021.

The time and cause of all-cause death (including the direct and chronic causes of death, such as severe pneumonia and dementia) were recorded.

The intervention group with decreased intrinsic capacity will go through a comprehensive assessment. Intervention group will be re-assessed at 3 months and 6 months after baseline, while the control group will be assessed at baseline and 6 months.

7. Benefits and risks of research

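### The only planned between-arm outcome comparison uses an unspecified propensity-matched set in a trial described as individually randomised, and names none of the five secondary scales

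*Combined protocol and SAP*

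**What the plan says.** Section 3 calls the study a prospective randomised controlled study, with participants "randomly assigned to the intervention group (n=500) and control group (n=1500"). Section 5.2 gives each eligible person a number from a random number table and allocates by the remainder on division by 3: "The random number divided by 3 is an integer, and the remaining 1 is the control group, and the remaining 2 is the intervention group". Both describe allocation person by person.

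Section 4.2 introduces the t test and Mann-Whitney U test for baseline clinical information. Its only sentence on comparing outcomes between arms is: "The intervention group and the control group were propensity matched, and the incidence of adverse health outcomes (all-cause death, falls, functional decline"). The sentence goes on to changes in quality of life, within and between groups. It gives no ratio, caliper, covariates, algorithm or method for matched data. No quality-of-life instrument is named in the document.

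Section 3.2 declares five secondary outcomes: ADL, MMSE, MNA-SF, SPPB and GDS-5.

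Section 6.3 sets the schedule ("Follow-up time: 3 Months, 6 Months from baseline"). For follow-up by telephone, family doctor visit and record review it says that "the ADL score, frailty scale score, and adverse health outcomes (falls, recurrent falls, severe falls, all-cause death) were recorded". In a separate paragraph the intervention group is re-assessed at 3 and 6 months, "while the control group will be assessed at baseline and 6 months". The instruments for that assessment are not listed.

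**The concern.** Randomisation already supports a direct comparison of everyone in the arm assigned, so matching is not needed to remove confounding. What it can do is leave out randomised controls. Because ratio, caliper and covariates are all open, the set that is analysed can also be settled after the data have been seen.

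The second problem is a mismatch between outcomes declared and outcomes analysed. The five scales in section 3.2 do not appear in section 4.2, and the events and quality of life in section 4.2 do not appear in section 3.2. Section 2 makes the effect on health outcomes one of the two main questions. Followed as written, the plan would answer it without a named comparison for most of the declared scales.

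**Working it through.** **1. Which secondary outcomes have a named comparison?**

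| Scale (section 3.2) | Named in 4.2? | Could enter through functional decline? |
|---|---|---|
| ADL | No | Possibly: recorded at follow-up under 6.3 |
| SPPB | No | Possibly: 6.1 says "a score of ≤ 9 points is considered as physical function decline" |
| MMSE | No | No |
| MNA-SF | No | No |
| GDS-5 | No | No |

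Read strictly, 0 of 5 are named. Read generously, 2 of 5 are covered and 3 of 5 are not.

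**2. The plan's own figure.** Section 4.1 gives 190 per group and 380 in total. From its inputs (126 people, 70% with decline, 5% loss), 126 / 0.70 / 0.95 = 189.5, rounded up to 190; 2 × 190 = 380. This reproduces, but it assumes no matching ratio and so does not settle what matching costs.

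**3. Precision under matching.** No ratio is stated, so the result is a range. Assumptions: every intervention participant is matched, and the covariates do not predict outcome. In SD units, SE = √(1/n₁ + 1/n₀). The difference detectable with 90% power at two-sided 0.05 is (1.96 + 1.2816) × SE. The last column is the power to detect 0.167 SD, the difference with 90% power when everyone is analysed: Φ(3.2416 / SE ratio − 1.96).

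| Set from 500:1,500 | Controls dropped | SE | SE ratio | Detectable (SD) | Power |
|---|---|---|---|---|---|
| All, or 1:3 | 0 | 0.0516 | 1.000 | 0.167 | 90% |
| 1:2 | 500 | 0.0548 | 1.061 | 0.178 | 86% |
| 1:1 | 1,000 | 0.0632 | 1.225 | 0.205 | 75% |

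**4. The section 5.2 rule.** The numbers 1 to 2,000 leave remainders 0, 1 and 2 in 666, 667 and 667 cases. If multiples of 3 are controls, the arms are 667:1,333, not 500:1,500. Matching all at 1:3 would need 3 × 667 = 2,001 controls and is impossible. At 1:1, 666 controls are dropped and the SE ratio is √(2/667) / √(1/667 + 1/1,333) = 1.155.

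**5. Illustration on falls.** Section 4.1 gives 3-year rates: "functional decline in the group with decline in intrinsic ability at 3-year follow-up was 16.4%, 55.3% and 64.8"%, in the order death, falls, functional decline. If the hazard is constant, an assumption the document does not support or exclude, the 6-month risk of falls is 1 − (1 − 0.553)^(1/6) = 12.6%. The 95% CI half-width at equal risks is 1.96 × √(0.1256 × 0.8744) × SE: 3.35 points for 500:1,500, 3.56 at 1:2 and 4.11 at 1:1.

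Keeping 500 of 1,500 controls at random moves the estimate with an SD of √[0.1256 × 0.8744 × (1/500 − 1/1,500)] = 1.2 points. This is the same loss seen another way, since √[(4.11/1.96)² − (3.35/1.96)²] is also 1.2. It must not be added to the wider interval.

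**The case against.** **Allocation may have been by community.** A parenthesis in section 4.1 labels the two groups as an intervention community and a control community, and controls are served by community doctors outside the intervention service. If so, matching has a purpose, and deleting it would remove the only stated control of imbalance. This does not show that allocation was by community, because sections 3 and 5.2 say otherwise. It does mean that the conflict must be resolved before the matching sentence is touched. This part stands and governs the fix.

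**The cost may be nil.** At section 3's own 1:3 allocation, matching everyone drops nobody. A reader might infer that the plan loses 22% in precision; the documents do not support that, because 1:1 matching is stated nowhere. Even a 1:1 set of 500 per group exceeds the 190 of section 4.1. This stands, and it leaves the open specification and the unnamed outcomes as the main points.

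**Quality of life may be a loose label for the scales.** This is possible, since no instrument is named, but nothing establishes it. The safe statement is that the scales are not named in section 4.2.

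**The scales may well be collected.** A reader might infer from the follow-up list in section 6.3 that SPPB and the other scales are not measured at 6 months. That list belongs to telephone, visit and record follow-up; the separate assessment at 6 months names no instruments. The documents leave the point open.

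**This is a feasibility pilot.** That is true, and the primary outcome is untouched.

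**Conclusion.** The point holds as a cheap improvement. Section 4.2's only between-arm outcome comparison relies on a matching step that individual randomisation makes unnecessary and that the plan does not specify. At least three of the five declared secondary scales have no named comparison.

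The loss of precision runs from 0% (1:3) through 6% (1:2) to 22% (1:1) in standard error from 500:1,500, and is 15.5% at 1:1 from 667:1,333. These figures assume that all intervention participants are matched and that the covariates do not predict outcome.

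A reader might go further and infer that matching biases the comparison or undermines the trial. The documents do not support this. With valid randomisation matching does not in itself introduce bias, and the recruitment, training and satisfaction targets that form the primary outcome do not depend on it. The harm is confined to the second aim.

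**What to change.** First reconcile the community wording in section 4.1 with the individual randomisation in section 5.2.

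If allocation was individual, replace the matching sentence in section 4.2 with text such as:

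> Participants will be analysed in the arm assigned. ADL, MMSE, MNA-SF, SPPB and GDS-5 at 6 months will be compared between arms by ANCOVA adjusting for the baseline value of the same score, where both arms have 6-month scores. Deaths, falls and functional decline (defined from one named scale and threshold) will be compared by risk difference adjusted for age and sex. Change within an arm is descriptive.

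GDS-5 is the instrument declared in section 3.2; section 6.1 uses GDS-15 or the Zung scale, and the two must be reconciled. Quality of life, if kept, needs a named instrument. A sentence is also needed on participants who die or have no 6-month score. Matching, if wanted, can stay as a labelled sensitivity analysis with ratio, caliper and covariates fixed in advance.

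If allocation was by community, do not simply delete matching: the analysis must account for clustering and for baseline imbalance.

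The cost is a revised paragraph and a little more analysis. There are two limits. The score comparisons depend on controls having these scores at 6 months, which section 6.3 does not make explicit; if collection is over and they are missing, no amendment can supply them. And section 4.2 is partly in the past tense: if outcome data have already been seen, the change must be reported as post hoc.

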$P < 0.05$ indicates that the difference is statistically significant.

5. Patient enrollment and exclusion criteria

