5.1 Inclusion and exclusion criteria for research subjects

Inclusion Criteria:

- (1) Screened as positive for intrinsic capacity declines.
- (2) Decline in intrinsic capacity confirmed by in-depth assessment in any of the domains described as: MMSE < 27 (for cognition), SPPB ≤ 9 (for locomotion), MNA-SF < 12 (for vitality we used nutrition as a proxy), GDS-5 ≥ 2 (for psychology we used depression as a proxy) or any vision impairment.
- (3) Signed form of consent and willingly participate in the pilot study.

Exclusion Criteria:

- (1) Negative results in their intrinsic capacity decline screening.
- (2) Severe hearing problems as the study was conducted during COVID-19 pandemics period and relied on telecare or remote sessions of intervention.

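### Section 4.2 names none of the five secondary scales listed in 3.2, and the protocol contradicts itself on which depression scale is measured

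*Combined protocol and SAP*

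**What the plan says.** The second main question in section 2 asks whether the approach makes a difference to health outcomes and resource use. Section 3.2 lists five scales as secondary outcomes: ADL ("measured by the activities of daily living (ADL) 14-questionnaire scale"), MMSE, MNA-SF, SPPB and a depression scale ("Psychological health - measured by geriatric depression scale-five items (GDS-5").

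Section 4.2 has two analysis statements. The first gives the t test or Mann-Whitney U test. It opens with the baseline data, and its methods are "selected according to the data type to compare the basic clinical information of patients". The second is the only one about outcomes: after propensity matching, the arms are compared on "the incidence of adverse health outcomes (all-cause death, falls, functional decline) and changes in quality of life", both within arm (self-control) and between arms. That sentence gives no scale, visit, test or effect measure. The section ends with one general rule, that P below 0.05 "indicates that the difference is statistically significant".

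On depression, 5.1 admits people on "GDS-5 ≥ 2 (for psychology we used depression as a proxy". Section 6.1 instead describes a different instrument ("the total score of the geriatric depression scale 15 item (GDS-15) is 15 points"), with the Zung scale as an alternative, and 6.2 uses GDS-15.

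Section 6.3 names ADL, frailty, falls and death as follow-up data. It has the intervention arm reassessed at 3 and 6 months and the control arm assessed at baseline and 6 months, without listing what those assessments contain.

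**The concern.** The outcomes listed to answer the second main question have no stated analysis. The choice of scale, of final value or change, of cut-off for decline, and of between-arm or within-arm comparison could all be made after results are seen, under a single P<0.05 rule.

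The depression outcome has a further problem, because the text contradicts itself. Someone following 6.1 would collect GDS-15 or Zung scores, while 3.2 promises GDS-5. The plan gives no rule for obtaining one from another.

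**Working it through.** **1. The plan's own figure.** In 4.1, "126 people with decline in function as the endpoint event were required". With 70% having a decline in intrinsic ability and 5% loss: 126 / 0.70 = 180; 180 / 0.95 = 189.5, rounded up to 190; 190 x 2 = 380. The plan's 190 and 380 reproduce. Functional decline is therefore the endpoint behind that minimum. This does not measure harm, since 2000 people are planned.

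**2. Each 3.2 scale set against the other sections.**

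| Scale in 3.2 | Described in 6.1 | Named for follow-up in 6.3 | Named in 4.2 outcome sentence | Best available cover in 4.2 |
|---|---|---|---|---|
| 14-item ADL | PSMS (6 items) and Lawton IADL (8 items) | Yes | No | Functional decline, undefined |
| SPPB | Yes | No | No | Functional decline, undefined |
| MMSE | Yes | No | No | Quality of life, undefined |
| MNA-SF | Yes | No | No | Quality of life, undefined |
| GDS-5 | No (GDS-15 or Zung) | No | No | Quality of life, undefined |

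Named in 4.2: 0 of 5. Possibly under functional decline: at most 2 of 5. The other 3 of 5 depend on reading quality of life as an umbrella term.

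**3. Whether the t test / Mann-Whitney rule fills the gap.** It is written for baseline characteristics. Borrowed for outcomes, it would still not say which scale, which visit, final value or change, or whether baseline is adjusted for.

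**4. Whether functional decline has a usable definition.** The nearest text is in 6.1, where an SPPB of 9 or less counts as decline in physical function. Section 5.1 uses the same cut-off as one route to entry. Anyone enrolled by that route already meets it at baseline, so it cannot identify new decline in them. ADL is the better-supported reading: 3.2 presents it as the measure of physical function and 6.3 names it at follow-up. No number of points lost is stated. PSMS 6 + Lawton IADL 8 = 14 matches the item count in 3.2, but the document never says the two together form that scale.

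**5. Depression scale, section by section.** GDS-5 in 3.2 (outcome) and 5.1 (entry, 2 or more); GDS-15 (5 or more) or Zung (standard score above 50) in 6.1; GDS-15 (5 or more) in 6.2. GDS-5 appears 0 times in 6.1.

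**6. Error rate if the general rule is applied.** Five tests at 0.05, assumed independent, with no true effect: 1 - 0.95^5 = 0.226, about a 23% chance of at least one P<0.05. Section 4.2 states no multiplicity rule.

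**7. Scores lost to death (illustration).** Assuming the plan's 16.4% three-year death rate applies at a constant hazard, six-month mortality is 1 - (1 - 0.164)^(1/6) = 0.0294. That is 500 x 0.0294 = 14.7 and 1500 x 0.0294 = 44.1 deaths.

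**The case against.** The strongest reply is that quality of life in 4.2, for which no instrument is named, is a loose term for the domains in 3.2. All five scales would then be covered. The text does not exclude this, so a reader who infers that MMSE, MNA-SF and GDS-5 lack a comparison on every possible reading goes too far. The reply is still weak: 7.1 treats functional state and quality of life as separate things, and an umbrella term would supply no scale, visit or test.

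Second, GDS-5 is part of the in-depth assessment that confirms eligibility in 5.1, and 6.1 refers to the case report form for the rating scales. That form was not supplied and may settle the matter. This stands as a limit: the documents do not show that GDS-5 is never measured. It does not remove the contradiction in the text.

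Third, a reader might infer that MMSE, MNA-SF and SPPB are not collected at follow-up. The documents do not support that. They are in 6.1 and are plausibly repeated at the 6-month assessment in both arms.

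Fourth, these are secondary outcomes of a feasibility pilot, and naming scales, visit and test would be enough to close the basic gap. That is fair, and it limits the weight of the point. Baseline adjustment goes further than the gap requires, but it uses baseline scores where these are already taken.

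**Conclusion.** The point holds in this form. None of the five secondary scales is named in the only outcome comparison; two are covered at best by one undefined term and three, weakly, by another. The depression instrument is contradictory across 3.2, 5.1, 6.1 and 6.2. Following 6.1 as written may leave the listed outcome unmeasured at follow-up or spread over scales that cannot be pooled, subject to what the case report form says. The SPPB entry cut-off cannot serve as the definition of decline for people enrolled on it.

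The 23% figure assumes five independent tests and shows only what the blanket P<0.05 rule would allow. The undefined terms and the unstated handling of missing scores are mostly missing detail; the depression-scale conflict is wrong as written. The primary feasibility outcome is untouched. The plan should be changed, but the point does not undermine the trial's main purpose.

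**What to change.** 1. **Depression scale.** Reconcile 3.2, 5.1, 6.1 and 6.2 so that the scale named in 3.2 is the outcome for every participant in both arms at baseline and month 6. If data are already collected (the document mixes tenses), report the scale actually used and do not pool scales. Which score should trigger care in 6.2 is for the sponsor to reconcile; no position is taken here.
2. **Analysis in 4.2.** Compare the month-6 total score of each 3.2 scale between arms, adjusted for its own baseline value, with 95% confidence intervals. Month 6 is the follow-up assessment that 6.3 gives to both arms. Label these results secondary and supportive, and give functional decline the same status if it is derived from ADL, so that one scale is not judged under two rules. Treat within-arm changes as descriptive only: people enter on poor scores, so some improvement is expected without any effect.
3. **Functional decline.** Define it as a change from baseline to month 6 on the 3.2 ADL scale, with the sponsor fixing the number of points before the arms are compared. Do not use the SPPB entry cut-off. The sponsor should confirm that PSMS and Lawton IADL together make up the 14-item scale.

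**Cost.** Mostly wording in 4.2 and 6.1, and confirmation in 6.3 that the five scales are part of the month-6 assessment. GDS-5 must be added at month 6 if absent, which is possible only if that visit has not happened. SPPB needs in-person contact, so people followed by telephone alone would need a visit or be missing. Scores exist only for survivors, so deaths should be reported by arm beside them; on the constant-hazard assumption above, about 15 of 500 and 44 of 1500.
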